In the process of developing treatments for temporomandibular joint dysfunction (TMD), Drs. Anthony Sims and Brendan Stack observed improvement in tic severity in patients with co-occurring TMD and tic disorders. Sims and Stack's observation has been reported in the medical literature (Sims & Stack, 2009), and multiple positive video testimonials of Tourette Syndrome patients successfully treated with an oral orthotic can be viewed on the internet (please see the URLs in the attachments). Sims and Stack posit that the mechanism by which the oral orthotic reduces TS symptoms is not within the striatal-thalamo-cortical-circuits commonly thought to be related to TS. Rather Sims and Stack believe that the tics of TS are reflexive muscle contractions (tics) related to irritation of peripheral nerves. The reflex occurs at the spinal cord level within the spinal trigeminal nucleus, specifically the subnucleus caudalis. They posit that, for some individuals, asynchronous development of the bone structure of the face during childhood leads to misalignment of the temporomandibular joint (TMJ). The misalignment results in irritation of the sensory afferent fibers of the trigeminal nerve leading to crosstalk (i.e. ephaptic transmission) at the level of the spinal cord within the subnucleus caudalis between the trigeminal nerve sensory fibers and motor efferent fibers in other cranial nerves and in the spinal motor tract more generally. Perhaps the simplest common example of the stimulation of a sensory nerve and a reflexive muscle contraction is when the corneal of the eye is irritated and a blink reflex occurs. The oral orthotic is thought to relieve the irritation of the trigeminal nerve, and thus alleviate tics. If oral orthotics are effective in reducing tic severity it will be a paradigm shift in the treatment of TS and in understanding the pathophysiology of TS. The first logical step to evaluate whether an oral orthotic can reduce tic severity is to conduct a pilot trial to establish whether a larger, definitive randomized controlled trial is feasible. The goal of this proposal is to conduct a 2 week randomized, blinded, controlled clinical feasibility trial to establish methods for a larger definitive clinical trial and for treatment responders to assess durability of treatment over an additional 10 week follow-up period (12 weeks total treatment). Perhaps the most critical aspect of the study's design is to fully establish procedures for the blinding of the treating clinician, patient and evaluator (blinding procedures detailed in the attachments). Without well established and effective blinding procedures there is a substantial risk that utility of this novel and potential controversial approach will not be realized. Though hundreds of children have been treated with this orthotic for tic disorders, these children were not treated in a controlled research environment. The data on this device is therefore strictly anecdotal. Our objective is to obtain pilot data on the efficacy of this device through a double blind, randomized, placebo controlled study in order to validate the potential benefit of this treatment option. This study is a double blind, randomized, placebo controlled trial. This protocol is designed as a feasibility trial: to ensure that our methods are sound before proceeding to a larger scale study. Our mission in this trial is two-fold: 1. To evaluate the feasibility of a 2-week randomized controlled trial of an active vs. sham occlusal splint to reduce tic severity. 2. To assess the durability of the occlusal splint among orthotic treatment responders over an additional 10 weeks.

STUDY DESIGN

The study is a 2 group, 2 week randomized controlled feasibility trial of an active vs sham oral orthotic to reduce tic severity in children and young adults ages 7-25 years. Responders to acute phase treatment will be followed for 10 additional week (12 weeks total) to assess intervention durability, safety and acceptability. Non-responders to the sham orthotic will be provided active treatment at the end of the 2 week acute phase. We aim to assess and enroll 24 participants; twelve participants will receive an orthotic adjusted to the appropriate therapeutic height, and twelve participants will receive an identical sham orthotic, but not adjusted to the recommended height for the given participant. An additional 6

participants will be enrolled in ABAB design of this study to further hone in on a potential mechanism of action of the occlusal splint by assessing changes in autonomic arousal as a result of wearing the device (procedural information below). This pilot will not be powered to determine efficacy or generate effect sizes, but will determine the feasibility of study procedures including recruitment, assessment, randomization, blinding, sample maintenance and acceptability and adherence to the orthotic treatment. Subjects will be required to obtain medical clearance from their treating dentist prior to participation. Population: The study will be enrolling subjects with both Tourette's Syndrome (TS) and Chronic Tic Disorder (CTD), which are both defined below: -For a person to be diagnosed with TS, he or she must meet the following criteria: A. The person must have both motor tics (for example, blinking or shrugging the shoulders) and vocal tics (for example, humming, clearing the throat, or yelling out a word or phrase), although they might not always happen at the same time. B. The person must have had tics for at least a year. The tics can occur many times a day (usually in bouts) nearly every day, or off and on, but there must not be a single tic-free period of more than 3 months. C. The person's tics must begin before he or she is 18 years of age. D. The person's symptoms must not be due to taking medicine or other drugs or to having another medical condition (for example, seizures, Huntington disease, or postviral encephalitis). -For a person to be diagnosed with a chronic tic disorder, he or she must meet the following criteria: A. The person must have one or more motor tics (for example, blinking or shrugging the shoulders) or vocal tics (for example, humming, clearing the throat, or yelling out a word or phrase), but not both B. The person must have tics that occur many times a day nearly every day or on and off throughout a period of more than a year. During this period, there must not be a single tic-free period of more than 3 months. C. The person's tics must start before he or she is 18 years of age. D. The person's symptoms must not be due to taking medicine or other drugs or to having a another medical condition (for example, seizures, Huntington disease, or postviral encephalitis).

To evaluate the feasibility of a 2 week randomized controlled trial of an active vs sham oral orthotic to reduce tic severity.

To assess the durability of the oral orthotic among oral orthotic treatment responders over an additional 10 weeks.

We aim to assess and enroll 24 participants; twelve participants will receive an orthotic adjusted to the appropriate therapeutic height, and twelve participants will receive an identical sham orthotic, but not adjusted to the recommended height for the given participant. We aim to assess and enroll an additional 8 participants in an ABAB design to further hone in on a potential mechanism of action of the occlusal splint. This pilot will not be powered to determine efficacy or generate effect sizes, but will determine the feasibility of study procedures including recruitment, assessment, randomization, blinding, sample maintenance and acceptability and adherence to the orthotic treatment.

INCLUSION AND EXCLUSION CRITERIA

Inclusion Criteria are as follows: 1. Age 7-25 inclusive. 2. Presence of motor and/or vocal tics for at least 12 months. 3. Tics are of at least moderate clinical severity as evidenced by a Yale Global Tic Severity score of 14 or higher for motor or vocal tics only and 22 or higher for Tourette syndrome and present during the baseline assessment. 4. IQ estimate of 70 or higher 5. Comorbid disorder (e.g., ADHD, OCD, ODD) will be allowed provided that the tic symptoms are of primary concern to parents and comorbid

symptoms are not of sufficient severity to require immediate treatment other than that provided by the current study. 6. Pre-existing stable medication (see protocol for details), tic or otherwise, will also be allowed provided the family agrees to refrain from med changes over the course of the acute phase of the study 7. Sufficient command of the English language to participate in informed consent and assessment procedures. 8. Agree for videotaping of study procedures 9. Clearance by treating dentist: Certification of good dental health provided by the subject's current dentist prior to enrollment in the study

Exclusion Criteria as follows: 1. Major psychiatric disorder at screening that would preclude full participation in study procedures including psychosis, mania, depression, untreated combined type ADHD, autism and pervasive developmental disorders. 2. Medication changes are planned during the acute and follow-up phase of treatment. 3. Other dental health problems that might interfere with the assessment, installation, or wearing of orthotic device. 4. Does not consent to being videotaped

DATA AND SAFETY MONITORING PLAN

The research does involve administration of physical stimuli other than auditory and visual stimuli associated with normal classroom situations; The occlusal splint is a removable dental appliance that fully covers the occlusal surface of the lower teeth. Distinct from a simple bruxism device (mouthguard), the splint for this study will have extra material built up vertically along the lower pre-molars and the molars. The height of this vertical build up is specific to each patient, as determined in an initial orthotic fitting session. Subjects will be fit for and given this oral orthotic to help with their tics. Subjects may find the fitting and/or the use of the orthotic to be uncomfortable, or otherwise foreign. Subjects will be told that they can take out the orthotic should it ever prove too uncomfortable.

The research does not involve any deprivation of physiological requirements such as nutrition or sleep, manipulation of psychological and/or social variables (i.e. sensory deprivation, social isolation, psychological stress, etc.).

The research does not involve any use of deceptive techniques without the knowledge of the subject.

The research does involve probing of information which might be considered personal or sensitive, including the examination of the medical record; The interviews during the course of the study involve no specific risk or discomfort beyond those of a standard clinical interview. However, parents and children will be asked to disclose personal information and to discuss potentially emotional topics related to the subject's symptoms, and the impact of these symptoms on the subject and his/her family. It is possible that some children and parents may become uncomfortable discussing such information during the assessments. All of our investigators are highly experienced clinicians that have been trained in administering such assessments, and monitoring distress in patients and subjects. Subjects will also not have to answer any questions that they do not feel comfortable answering.

The research does not involve any presentation to the subject of any materials which they might find to be offensive, threatening or degrading.

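### Does the aim to validate the splint's benefit contradict a pilot that the protocol says is not powered for efficacy?

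*Protocol*

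**What the plan says.** The Protocol's opening narrative notes that existing evidence on the device is anecdotal, and continues: "Our objective is to obtain pilot data on the efficacy of this device through a double blind, randomized, placebo controlled study", with the purpose clause "in order to validate the potential benefit of this treatment option". The same paragraph earlier gives the goal of the proposal as a feasibility trial to work out methods for a later definitive one. Directly after the sentence at issue, it again calls the study a feasibility trial. It then numbers two aims: feasibility of the 2-week randomised comparison, and durability in responders over a further 10 weeks.

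The Study Design section states: "This pilot will not be powered to determine efficacy or generate effect sizes, but will determine the feasibility of study procedures". The statement of sample size before the Inclusion and Exclusion Criteria repeats this. The feasibility and durability aims are also restated between these two places.

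**The concern.** The sentence opens by naming an objective and ends with the verb validate. Set beside a disclaimer of power for efficacy, it reads as though the trial has two purposes that cannot both be met. If it governed interpretation, a chance difference at week 2 could be reported as meeting the objective and a null result as failing it, although a comparison of this size would support neither reading reliably. The protocol describes the approach as novel and possibly controversial, so over-reading a small pilot would have a real cost.

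**Working it through.** **The wording.**

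1. The objective sentence is qualified twice: the data are pilot data, and the benefit is potential. The word that overreaches is validate.
2. The disclaimer concerns power. It does not say that no efficacy data will be collected. Collecting outcome data in a pilot is compatible with lacking power to draw a conclusion from them.
3. The statements of purpose compare as follows.

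| Place in Protocol | Stated purpose |
|---|---|
| Opening narrative, goal of the proposal | Feasibility trial to establish methods; durability in responders |
| Opening narrative, sentence at issue | Pilot efficacy data, to validate potential benefit |
| Opening narrative, numbered aims | Feasibility; durability |
| End of Study Design and following text, restated aims | Feasibility; durability |
| Study Design, and again in the sample statement | Not powered for efficacy or effect sizes; determines feasibility |

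Only one of these entries leans towards efficacy. No efficacy hypothesis, alpha, test or success criterion is attached to it in the text shown.

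**The arithmetic.** The protocol gives no power figure to reproduce. Its only inputs are the total ("We aim to assess and enroll 24 participants") and the equal split in Study Design, with 12 in the active arm and 12 in the sham arm; 12 + 12 = 24, so these agree. The following are assumptions, not protocol content: two-sided 5%, two-sample t-test, equal variances, no dropout, standardised differences d from 0.3 to 1.2.

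- Detectable difference at 80% power, normal approximation: (1.960 + 0.842) × √(2/12) = 2.802 × 0.408 = 1.14 SD. With the exact noncentral t it is 1.20 SD. At 90% power it is 1.39 SD.
- Power at 12 per arm (noncentral t), and n per arm for 80% power (normal approximation):

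| d | Power | n per arm for 80% |
|---|---|---|
| 0.3 | 11% | 175 |
| 0.5 | 22% | 63 |
| 0.8 | 47% | 25 |
| 1.0 | 65% | 16 |
| 1.2 | 80% | 11 |

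- The last entry is 11 and not 12 because the normal approximation is slightly optimistic at this size.
- Half-width of the 95% interval for the mean difference, in SD units: t(22; 0.975) × √(2/12) = 2.074 × 0.408 = 0.85.
- For an observed standardised difference of 0.5: SE = √(2/12 + 0.5²/48) = √0.1719 = 0.415, so the interval is 0.5 ± 1.96 × 0.415, or −0.31 to 1.31.
- For a binary response of 50% against 20%, power is 33% (normal approximation) or 21% (Fisher). For 60% against 20% it is 52% or 39%.

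These results say what the protocol already says: the comparison is too small for conclusions about efficacy unless the effect is very large.

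**The case for a change.** The best argument for a change is that validate and unpowered do not belong together. The sentence is the one introduced as the objective, and it follows directly on the remark about anecdotal evidence, so a reader may take the randomised comparison as the evidence that replaces anecdote. Later follow-up cannot strengthen that comparison: after week 2 only responders are followed, and sham non-responders are offered active treatment. Objectives are protocol content, so a separate statistical analysis plan would not excuse the wording, and correcting it would cost one clause.

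The criticism of the verb stands. The claim that the sentence governs what may be concluded does not. Anyone reporting validated benefit would have to set aside two explicit disclaimers and every formal statement of the aims. Further rules, such as barring a hypothesis test at week 2 or prescribing descriptive intervals only, belong in the analysis plan, which is not shown, and statisticians could reasonably differ on them. A rule against using the estimate to size the definitive trial would largely repeat the existing disclaimer about effect sizes.

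**Conclusion.** There is a tension of wording in one narrative sentence, and no conflict between the formal aims and the design. The protocol states the limitation itself, in two places, and the calculation supports it: 80% power only at about 1.2 SD, and 11% to 47% across d = 0.3 to 0.8. Those figures rest on the assumed two-sided 5% t-test with no dropout; losses would lower them and reinforce the disclaimer. It would also be too strong to say that 12 per arm can show nothing, since an effect of 1.2 SD or more would be detected with at least 80% power.

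The sponsor could soften the verb if the document is amended for another reason. Doing so would leave the sample size, procedures, analysis and permissible conclusions as they are, so no change is required.

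### Does the protocol leave open whether sham-arm responders, or sham non-responders switched to the active splint, count towards the durability aim?

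*Protocol*

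**What the plan says.** The Protocol describes weeks 2 to 12 in four places.

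- Opening background, statement of the goal: "for treatment responders to assess durability of treatment over an additional 10 week follow-up period (12 weeks total treatment").
- Opening background, second item of the two-part mission: "To assess the durability of the occlusal splint among orthotic treatment responders over an additional 10 weeks".
- Study Design section: "Responders to acute phase treatment will be followed for 10 additional week (12 weeks total) to assess intervention durability, safety and acceptability".
- Second objective, just before the sample-size paragraph: "To assess the durability of the oral orthotic among oral orthotic treatment responders over an additional 10 weeks".

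The Study Design section then adds: "Non-responders to the sham orthotic will be provided active treatment at the end of the 2 week acute phase".

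The device words cover both arms. Study Design calls the trial a "randomized controlled feasibility trial of an active vs sham oral orthotic to reduce tic severity", and the mission describes a "randomized controlled trial of an active vs. sham occlusal splint to reduce tic severity". The randomised sample is 24: "We aim to assess and enroll 24 participants; twelve participants will receive an orthotic adjusted to the appropriate therapeutic height", and twelve receive the sham. The protocol states that the pilot has no power for efficacy or for estimating effects, and that its outputs concern feasibility, including how acceptable the device is and how well it is worn.

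**The concern.** The follow-up population is worded four ways, and no wording says active arm or sham arm. Since both device terms are used for the active and the sham device, an aim about the durability of the orthotic among its responders can be read as active-arm responders only or as responders of either arm. On the second reading, a summary of the device's durability would include people whose improvement came on the sham.

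The switched group raises a second question. Sham non-responders start active treatment at week 2, and no sentence in the text at hand says whether they are then followed. By week 12 they can have had at most 10 weeks on active, against 12 for an active-arm responder. Yet acceptability and adherence are feasibility outputs, and this group would supply information on both.

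At stake is the denominator, and to some degree the meaning, of the second of only two aims. Who enters a follow-up phase is participant flow, which a protocol normally settles itself, so it is fair to ask whether this one does.

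**Working it through.** **1. The plan's own figures.** Randomised sample: 12 + 12 = 24, as stated. Duration: 2 + 10 = 12 weeks, as stated. The protocol gives no response rate, effect size or power, so there is no sample-size calculation to reproduce.

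**2. The statements side by side.**

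| Place | Whom it names | Arm named? | Kind of statement |
|---|---|---|---|
| Background, goal | responders to treatment | no | aim |
| Background, mission item 2 | responders to the orthotic | no | aim |
| Study Design | responders in the acute phase | no | who is followed |
| Second objective | responders to the oral orthotic | no | aim |

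Only the Study Design sentence says who is followed. It has no restriction by arm, and the sentence after it moves only the sham non-responders to active treatment. Together they give this flow:

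- Active responder at week 2: followed.
- Sham responder at week 2: followed.
- Sham non-responder at week 2: given active treatment. This person is not an acute-phase responder and so is outside the durability follow-up as worded.

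The three aim statements fit this flow precisely because the device words cover both arms. The active-only reading arises only when an aim is read apart from Study Design.

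**3. Size of the open choice.** Assumed response rates, not in the protocol: active 25%, 50%, 67%; sham 10%, 25%, 33%. With 12 per arm, rounded to whole people:

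- Active responders: 12 × 0.25 = 3; 12 × 0.50 = 6; 12 × 0.67 ≈ 8.
- Sham responders: 12 × 0.10 ≈ 1; 12 × 0.25 = 3; 12 × 0.33 ≈ 4.
- Active responders only: 3 to 8 people, 6 at the midpoint.
- Responders of either arm: 3 + 1 = 4 to 8 + 4 = 12 people, 6 + 3 = 9 at the midpoint.
- Sham share of all responders: 1/(8 + 1) = 11% to 4/(3 + 4) = 57%; midpoint 3/9 = 33%. The 57% needs sham response (33%) to exceed active response (25%).

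**4. The switched group.** Sham non-responders number 12 − 4 = 8 to 12 − 1 = 11, and 9 at the midpoint. Adding all of them to the responders would give 3 + 12 = 15 to 8 + 12 = 20 people, but no reading of the text yields that cohort, because every statement is limited to responders. The 12 weeks of total treatment is attached to responders and is never applied to this group. Its 12 − 2 = 10 weeks on active is therefore not a discrepancy.

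**The case for a change.** The strongest case for a change is that an SAP can supply analysis methods but should not have to decide whom a stated aim concerns. The protocol worded the population four ways and tied none to an arm. If sham responders are followed, as Study Design implies, then an aim about the durability of the orthotic takes in sham responses. At the assumed midpoint that is 3 of 9 people. The objectives also do not repeat the acute-phase limit, so someone who responds later, after switching to active, might be read in.

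Part of this stands. No sentence says outright whether sham responders count towards durability, and the text at hand does not say whether switched participants are followed at all.

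The rest is weaker. Different words for the same people are not a contradiction, and Study Design supplies the flow. Silence about the switched group's visits is thin evidence, because the text shown has no visit schedule for any group and refers to attachments and procedural detail that do not appear in it. Reporting by arm, keeping switched participants apart and choosing their time origin are matters commonly left to an SAP, and the SAP is not shown here.

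**Conclusion.** The concern does not call for a change. The half about switched sham non-responders fails on the wording, since Study Design confines the durability follow-up to acute-phase responders and so excludes them. The half about sham responders is a real but small looseness: the follow-up rule takes in both arms, and the aims do not say whether durability is summarised for both.

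This is a gap that analysts fill sensibly. With at most 12 people per arm and no power claimed, the follow-up can only be descriptive. Listing responders by randomised arm answers the active-only question and the either-arm question from the same data, and nothing in the protocol says that the arms will be pooled. If the rule is followed as written, no data are lost under either reading.

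The size is 6 against 9 people at assumed response of 50% active and 25% sham, and 3 to 8 against 4 to 12 over the assumed ranges. These counts rest wholly on assumed rates. No test, sample size or stated figure depends on the choice.

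### Eligibility neither excludes nor records earlier use of this height-adjusted orthotic for tics, so a few participants may be able to recognise their device, in a pilot whose central aim is to establish blinding

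*Protocol*

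**What the plan says.** The Protocol's section on inclusion and exclusion criteria has nine inclusion and four exclusion items. Four of them come near the subject of prior treatment or the mouth:

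- Exclusion 3: "Other dental health problems that might interfere with the assessment, installation, or wearing of orthotic device".
- Inclusion 9, on clearance by the dentist: "Certification of good dental health provided by the subject's current dentist prior to enrollment in the study".
- Inclusion 6: "Pre-existing stable medication (see protocol for details), tic or otherwise, will also be allowed".
- Exclusion 2: "Medication changes are planned during the acute and follow-up phase of treatment".

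The first two concern dental health and the last two concern medication. No item, and no other part of the text shown, bars or records past or current use of an oral orthotic.

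Three further statements bear on the point. The opening background text says "Though hundreds of children have been treated with this orthotic for tic disorders", and adds that "multiple positive video testimonials of Tourette Syndrome patients successfully treated with an oral orthotic can be viewed on the internet". The same text says of the design: "Perhaps the most critical aspect of the study's design is to fully establish procedures for the blinding of the treating clinician, patient and evaluator". The Study Design section describes the comparator this way: "twelve participants will receive an identical sham orthotic, but not adjusted to the recommended height for the given participant". Blinding is also named there among the feasibility matters that the pilot is meant to settle.

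**The concern.** Active and sham devices are described as the same appliance, with height as the one stated difference. A participant who has never worn the device has nothing to compare it with. A participant who has worn it at an individually adjusted height has a direct reference for that one feature, and also remembers what happened to their tics. The Protocol itself reports that such people exist, and nothing in the eligibility list keeps them out on that ground.

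What is at stake is mainly the pilot's own product. If participants' guesses about their allocation turn out better than chance, the sponsor will want to know whether the blinding procedure needs redesign before a larger trial. If some participants had worn the device before and nobody recorded it, that question cannot be answered from the data.

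**Working it through.** **Step 1. Can a former user enter?** Taking the criteria in turn for a dentally healthy person who once wore the orthotic for tics:

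- Inclusion 9 and Exclusion 3 do not stop this person, because both turn on dental problems.
- Inclusion 6 and Exclusion 2 do not stop this person, because both turn on medication.
- Inclusion 3 requires tics at baseline with a Yale Global Tic Severity score of at least 14 (motor or vocal tics only) or 22 (Tourette syndrome). It removes former users whose tics remain controlled below those values. It does not remove those who relapsed, responded partly or failed to respond.
- The other items (age, tic duration, IQ, comorbidity, language, videotaping) do not bear on the matter.

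So the rule admits some former users, though not all.

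**Step 2. Effect on a blinding assessment.** The Protocol gives no figure to reproduce here. The text shown does not say how blinding will be judged, so assume that each participant guesses the allocation. Inputs: n = 12 in the sham arm (Study Design). Let k sham participants know their arm, and let the others guess at 50/50. Then

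expected share correct = (k + (12 − k) × 0.5) / 12

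and the arm's blinding index (share correct minus share incorrect) is k/12.

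| k | Expected correct | Share | Index |
|---|---|---|---|
| 0 | 6.0 | 50% | 0 |
| 1 | 1 + 11 × 0.5 = 6.5 | 54% | 0.08 |
| 2 | 2 + 10 × 0.5 = 7.0 | 58% | 0.17 |
| 3 | 3 + 9 × 0.5 = 7.5 | 63% | 0.25 |

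One person is 1/12 = 8.3% of an arm, but the expected share of correct guesses moves by only half of that, 4.2 points, because a guesser would be right half the time anyway. Two people move it by 8.3 points. For scale, the standard error of a proportion of 50% with n = 12 is √(0.25/12) = 0.144, about 14 points.

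**Step 3. How likely is it that any former user enrols?** The Protocol does not give the share p of former users among those enrolled. As an illustration only, assuming independent enrolment, P(at least one) = 1 − (1 − p)^n:

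| Assumed p | Among 24 randomised | In the sham arm of 12 |
|---|---|---|
| 1% | 21% | 11% |
| 2% | 38% | 22% |
| 5% | 71% | 46% |
| 10% | 92% | 72% |

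**Step 4. After the fix.** With former users of this orthotic excluded, the number who could recognise the sham from having worn the same kind of device for tics is 0 of 24 by design. The 12 + 12 allocation is unchanged.

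**The case against.** The other side has several good arguments.

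- **Unknown numbers.** The Protocol says that hundreds of children were treated. It does not say where or when, or whether any would seek a trial with a sham arm. The count may be zero. This stands, and it limits how firmly the point can be put.
- **All former users admitted.** A reader might infer that the criteria let in everyone who has worn the device. They do not, because the severity threshold in Inclusion 3 turns away those who are doing well. Relapsed, partial and failed responders remain.
- **Blinding defeated.** A reader might also infer that former users would break the blind and leave the result uninterpretable. The documents do not support that. Recognition by height is plausible but not shown, height is set afresh for each patient at the fitting session (Data and Safety Monitoring Plan), and the blinding procedures are in attachments not available here. At one or two participants the shift is well inside the sampling error of a 12-person arm. The attachments may reduce the risk, but a procedure cannot remove a participant's memory of the device, and it does not alter the eligibility list.
- **Biased treatment comparison.** It is tempting to say that tic ratings would be biased between arms. Randomisation balances former users in expectation, an evaluator blind is planned, and the pilot is declared not powered for efficacy or effect sizes. What remains is the effect of unblinding itself and chance imbalance in a small sample.
- **Too wide an exclusion.** Barring everyone who ever had a splint for temporomandibular dysfunction could remove part of the population in which the hypothesis arose. This stands, and the fix below is narrower for that reason.
- **ABAB participants re-entering.** The Protocol calls them additional to the randomised sample, so a separate rule against their crossing into it would add little.

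**Conclusion.** The gap is real. The eligibility rule neither excludes nor records prior use of the treatment under test, although the Protocol reports that former users exist and treats blinding as central. The likely consequence is a modest upward shift in correct guesses, which makes blinding look weaker than the procedure deserves, and difficulty in saying why. In a 12-person sham arm the expected share of correct guesses is 54% with one knowing participant and 58% with two, against 50% with none.

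These figures assume that a former user recognises the sham with certainty, that the others guess at random, and that guesses are collected from participants. Less than certain recognition would make the shift smaller. How many former users would enrol is an assumption throughout, with zero as a possible value. The point is worth correcting because the correction is cheap and protects the result that the pilot exists to deliver.

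**What to change.** 1. Add one exclusion criterion: previous use of this or an equivalent height-adjusted oral orthotic given for tics.
2. Add one screening question on any other occlusal splint or similar appliance, for example one given for temporomandibular dysfunction. Record the answer without making it a bar to entry.
3. Report the blinding assessment by that recorded prior use.

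The cost is one line in the criteria, one item on the screening form and one extra split in a descriptive table. The recruitment pool becomes somewhat smaller, by an amount that the Protocol gives no means to estimate. Recruitment is itself a feasibility question here, so the number turned away under the new criterion should be counted in the screening log.
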